3.5 Participant Withdrawal and Replacement

Over the course of the study, the Sponsor and the Investigator or designee may withdraw any participant from the study for one of the reasons described below; participant withdrawal will be done in accordance with the clinical site's SOP:

- Safety reason;
- Non-compliance with protocol requirements;
- Significant protocol deviation;
- Positive pregnancy test, drug screen, cotinine test, or alcohol breath test;
- Vomiting within 4 hours post-dose;
- Positive COVID-19 test.

Participants excluded from dosing in one period as per criteria listed above, may be invited to participate in subsequent periods of the study if deemed appropriate by the Investigator and appropriate from a statistical standpoint (i.e., would permit adequate statistical comparison). However, participants with positive pregnancy test, COVID-19 test, drug screen, cotinine test, or alcohol breath test will be definitively withdrawn from the study.

Participants experiencing emesis following study drug administration may be withdrawn. An evaluation will be done on a case-by-case basis in order to decide if withdrawal is appropriate.

Participants who withdraw, or are withdrawn, prior to dosing may be replaced. Participants who withdraw, or are withdrawn, from the study after dosing will not be replaced.

This document is confidential.

4 CHANGES FROM THE PROTOCOL

There are no changes in planned analyses compared to the protocol.

5 PHARMACOKINETIC AND SAFETY PARAMETERS

For PK analyses, AUC_{last} , AUC_{inf} , and C_{max} calculated using zavegepant concentration data will be the primary endpoints. $AUC_{extrap\%}$, T_{max} , $T_{1/2}$, K_{el} , V_z/F and CL/F for zavegepant will be secondary endpoints; reference [section 11.3](#).

Safety and tolerability parameters are secondary endpoints; reference [section 10](#).

This document is confidential.

6 ANALYSIS POPULATIONS

All participants' inclusion status into each analysis population will be determined after database lock for the final analysis.

6.1 Screened Population

The screened population will include all participant who sign the informed consent form.

6.2 Randomized Population

The randomized population will include all participants who are randomized.

6.3 Safety Population

The safety population is defined as all participants who receive at least one dose of any study drug. In each period, participants will be analyzed according to treatment received.

6.4 Pharmacokinetic Population

The PK population will include all participants from the safety population who receive at least one dose of zavegeptan, and for whom the PK profile can be adequately characterized. The PK population will be used for calculation of PK parameters.

6.5 Pharmacokinetic Statistical Population

The PK statistical population will include all participants from the PK population who complete at least one period of treatment for at least one PK parameter and who have not experienced any protocol deviations or other circumstances to exclude the participant from the PK statistical analysis.

A participant with pre-dose concentrations may be excluded from descriptive statistics and ANOVA if the pre-dose concentration is greater than 5% of the C_{max} value for that participant. A participant may be excluded from the descriptive statistics and ANOVA if the participant has experienced emesis within 2 times median T_{max} for a given treatment. For the period where this would apply as appropriate, data (concentrations and PK parameters) from these participants will be presented in data listings but excluded from the statistical analyses.

This document is confidential.

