4.4 Subject Withdrawal and Replacement

Subjects will be advised that they are free to withdraw from the study at any time. Over the course of the study, the Sponsor and the Investigator or designee may withdraw any subject from the study for one of the reasons described below; subject withdrawal will be done in accordance with the clinical site's Standard Operating Procedure (SOP):

- Safety reason;
- Non-compliance with protocol requirements;
- Significant protocol deviation;
- Positive pregnancy test, drug screen, cotinine test, or alcohol breath test;
- Vomiting within 4 hours post-dose;
- Positive test result for COVID-19 (during any study period).

Clinical laboratory results will be reviewed by the Investigator or designee prior to each dosing and subjects will be withdrawn from the study if it is deemed that the subject's safety may be at risk on the basis of these test results.

Subjects excluded from dosing in one period as per criteria listed above, may be invited to participate in subsequent periods of the study if deemed appropriate by the Investigator and appropriate from a statistical standpoint (i.e., would permit adequate statistical comparison). However, subjects with positive pregnancy test, COVID-19 test, drug screen, cotinine test, or alcohol breath test, will be definitively withdrawn from the study.

Subjects who withdraw prior to dosing may be replaced.

Subjects who withdraw or are withdrawn after study drug administration will be asked to remain at the clinic until the Investigator or designee agrees that the subject is fine and can be discharged. As soon as subject withdrawal is confirmed, blood sampling will be stopped. A PK blood sample may be collected at the time of withdrawal if deemed required by the Investigator. Study Exit or ET procedures will be performed at the time of withdrawal from the study or as soon as possible thereafter.

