11.3 PK Parameters

Blood samples will be collected for zavegeptan PK analysis at pre-dose (within 1 hour prior to dosing), and 0.25, 0.5, 1, 1.5, 2, 2.5, 3, 4, 5, 6, 8, 10, 12, 16, and 24 hours post-dose in each period. Bioanalysis of all associated plasma samples should be completed prior to the initiation of the PK and statistical analyses. Analysis will be performed using a fully-validated analytical method by a qualified bioanalytical laboratory.

The following PK parameters will be calculated, based on the PK population, by standard non-compartmental methods using the plasma concentrations of zavegeptan.

Parameter	Definition
AUC _{last}	area under the concentration-time curve from time zero until the last observed concentration
AUC _{inf}	area under the concentration-time curve from time zero to infinity (extrapolated)
AUC _{extrap%}	percentage of AUC _{0-inf} due to extrapolation from the time of the last observed concentration to infinity, calculated as $[1 - (AUC_{last}/AUC_{inf})] \times 100$
C _{max}	maximal observed concentration
T _{max}	time when the maximal concentration is observed
T _{1/2}	terminal elimination half-life
K _{el}	terminal elimination rate constant
CL/F	apparent clearance
V _z /F	apparent volume of distribution

PK of Treatment C (AUCs and C_{max}) will be normalized to a dose of 100 mg.

Additional PK parameters may be calculated.

Note: AUC parameters will be calculated using linear up log down trapezoidal method, where the linear trapezoidal rule is used any time the concentration data is increasing, and the logarithmic trapezoidal rule is used any time that the concentration data is decreasing.

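### Would an AUClast cut short by withdrawal after vomiting distort the primary comparison?

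*SAP*

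**What the plan says.** SAP 5 says that AUClast, AUCinf and Cmax "calculated using zavegepant concentration data will be the primary endpoints". SAP 11.3 defines AUClast as the "area under the concentration-time curve from time zero until the last observed concentration" and sets no minimum last sampling time.

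Protocol 4.4 lists "Vomiting within 4 hours post-dose" among the reasons for which a subject may be withdrawn, and adds: "As soon as subject withdrawal is confirmed, blood sampling will be stopped". It also allows one further PK sample at the time of withdrawal. SAP 3.5 repeats the list and states that "Participants experiencing emesis following study drug administration may be withdrawn", after a case-by-case evaluation.

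The analysis rule for emesis is in SAP 6.5: "A participant may be excluded from the descriptive statistics and ANOVA if the participant has experienced emesis within 2 times median" Tmax for the treatment concerned. For the period affected, data "from these participants will be presented in data listings but excluded from the statistical analyses", where appropriate.

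SAP 11.3 has two firm rules for incomplete profiles. If Kel cannot be estimated, or if AUCextrap% exceeds 20%, then AUCinf, AUCextrap%, T1/2, CL/F and Vz/F are flagged and removed. Neither list includes AUClast.

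Three general provisions also apply:
- SAP 6.4 limits the PK population to those "for whom the PK profile can be adequately characterized".
- SAP 6.5 excludes participants with protocol deviations or other circumstances that warrant it.
- SAP 11.3 lets the pharmacokineticist, with Sponsor agreement, leave a parameter uncalculated when the concentration data do not support it.

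**The concern.** The conduct rule counts 4 hours from dosing, whereas the analysis exclusion counts twice the median Tmax. If a treatment's median Tmax is below 2 hours, a participant could vomit after the exclusion window closes but before 4 hours, be withdrawn, and have sampling stopped. AUCinf for that period would go by rule, but no sentence removes AUClast. SAP 14 does not fill in missing concentrations, so a fraction of the true area would enter the ANOVA as if complete.

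The 4-hour route is not the only one. The emesis sentence in SAP 3.5 has no time limit, and any withdrawal in mid-period stops sampling whatever the Tmax.

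A kept partial area lowers the geometric mean of the affected treatment. In a test treatment it pulls one ratio down; in Treatment D it pushes all three up. The two AUC endpoints would then rest on different sets of periods. The provisions that could prevent this are matters of judgement, applied after database lock (SAP 6) in an open-label study.

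**Working it through.** **1. The plan's own figure.** SAP 3.4 assumes a CV of 40%, a true ratio of 1.0 and 52 participants.

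- Within-subject SD on the log scale: √ln(1 + 0.40²) = √ln 1.16 = 0.3853.
- SE of a log ratio: 0.3853 × √(2/52) = 0.0756.
- Half-width with t(0.95; 150 df) = 1.655: 1.655 × 0.0756 = 0.125.
- Width on the ratio scale: exp(0.125) − exp(−0.125) = 0.251, which agrees with the stated 0.25.

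**2. The two windows.** Twice the median Tmax is 1, 2, 3 or 4 h for a median of 0.5, 1, 1.5 or 2 h. The part of the 4-hour window left uncovered is therefore 3, 2, 1 or 0 h. The documents give no Tmax, so whether any interval is uncovered is unknown.

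**3. How much area a stopped profile holds.** The kinetics are assumed, for scale only: one compartment, oral dosing, Tmax 0.5 to 1.5 h, half-life 2 to 8 h, the planned sampling times and the linear-up log-down rule. With ke = ln 2 / half-life, ka solves ln(ka/ke)/(ka − ke) = Tmax. Let f be the area to the last sample divided by AUC0-24. Drug lost through vomiting is ignored.

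| Tmax, half-life | Last sample | f | AUCextrap% |
|---|---|---|---|
| 1 h, 5 h (middle case; ka = 3.31/h) | 3 h | 0.32 | 69 |
| 1 h, 8 h (lowest f) | 2 h | 0.16 | 86 |
| 0.5 h, 2 h (highest f) | 4 h | 0.73 | 27 |
| 1 h, 5 h | 16 h | 0.92 | 11 |

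The first three rows all exceed 20% extrapolation. Full 24 h profiles on this grid extrapolate at most 13%. Stopping at 2 to 4 h would thus always trigger the removal and flagging of AUCinf.

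**4. Effect of one kept profile.** If the participant returns for the later periods, the design is balanced and the log ratio moves by ln(f)/52.

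- f = 0.32: −1.139/52 = −0.0219, or −2.2%. This is 0.0219/0.125 = 18% of the half-width and 0.0219/0.0756 = 0.29 SE.
- f = 0.16 (0.158 unrounded): −1.845/52 = −0.0355, or −3.5%.
- f = 0.73 (0.732 unrounded): −0.312/52 = −0.0060, or −0.6%.
- The same f = 0.32 in Treatment D: +2.2% on all three ratios.

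If the participant leaves for good, a generalised least squares fit of the SAP model without the interaction (two groups of 26 and between-subject SD 0.3 or 0.5 assumed) gave −1.5% to −2.2% for f = 0.32.

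**5. Effect of dropping the profile instead.** Losing one participant from a comparison gives SE = 0.3853 × √(2/51) = 0.0763 and a width of 0.253 instead of 0.251. Precision therefore gives no reason to keep a truncated value.

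**6. What has to happen for harm.** The vomiting must fall outside the exclusion window. The discretionary decision must be to withdraw. Sampling must stop early. The analyst must then keep AUClast for a profile already flagged as unfit for AUCinf, with three provisions available for leaving it out.

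**The case for a change.** The strongest case for a change is that none of the three provisions is a firm rule for a single period. Adequate characterisation has no criterion and is decided per participant, so someone with three full periods can qualify. The clause on other circumstances is open-ended and also per participant. The pharmacokineticist's discretion concerns parameters that cannot sensibly be calculated, and AUClast can always be calculated. SAP 7 allows a preliminary PK summary once final concentrations are available, so the judgement could be made with results in view. With f = 0.32, four affected Treatment B profiles would move B/D by exp(4 × ln 0.32/52) − 1 = −8.4%, about 70% of the half-width, and a sentence in the SAP costs little.

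Part of this stands: the text contains no express rule, and the choice is one of judgement. The multi-profile figure has no support in the documents. The nearest figure, in Protocol 1.2.2, is 13 of 364 (3.6%) stopping for any adverse event over eight weeks of daily 4 x 25 mg capsules. Applied to 52 that is 1.9 participants, for all causes and a much longer exposure. The regimens differ, so this gives scale only. Treatment D figures also assume a Tmax for an enteric-coated capsule that the documents do not supply.

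Nor would the judgement be hidden. The SAP lists population status, reasons for discontinuation and flagged parameters by participant, so a reader could see any retained partial area.

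The obvious rule, dropping both AUCs whenever withdrawal stops sampling, would do some harm. The 16 h profile in the table holds 92% of AUC0-24, extrapolates 11% and passes the SAP's own 20% limit, yet would be deleted. A narrower rule tied to that limit would be harmless, but it would only write down what the analyst can already do.

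**Conclusion.** No change follows. The omission is real: no sentence removes an AUClast cut short by withdrawal. But the plan does not prescribe keeping it either. The 4-hour criterion guides conduct at the clinic and the multiple of Tmax guides analysis once the data are in, so they do not contradict each other. Between them sits a gap that the general provisions in SAP 6.4, 6.5 and 11.3 allow the analyst to fill sensibly, prompted by the flag that an early stop would raise.

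The likely effect is nil or small. One retained test profile would move a ratio by −0.6% to −3.5%, or −2.2% in the middle case, and the documents state no acceptance limit that such a shift could cross. These sizes rest on an assumed one-compartment model, Tmax 0.5 to 1.5 h, half-life 2 to 8 h and a last sample at 2 to 4 h. For vomiting within 4 hours, they also need a median Tmax below 2 h. Several truncated profiles kept in the same treatment would matter more, but nothing in the documents points to that many.

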7 INTERIM ANALYSIS

No formal interim analysis is planned. However, a preliminary descriptive PK analysis may be performed when the final PK concentration data will be available. For this analysis, the scheduled times could be used in the calculation of the PK parameters.

This document is confidential.

8 SCHEDULE OF ANALYSIS

The final statistical analysis will be performed once all participants completed the study, the bioanalysis of all samples are complete and the database is locked.

This document is confidential.

9 STUDY POPULATION AND EXPOSURE

Each participant's inclusion or exclusion from each analysis population will be presented in a data listing. The study drug administration details, including date and time of administrations, will also be listed by participant.

9.1 Participant Disposition

The number of participants who were screened, screened failures, who were enrolled, who were randomized, who were dosed, who completed the study, and who were discontinued from the study and reasons for discontinuation, will be summarized. This summary table will also include the number of participants in each analysis population. The data (frequency and the percentage of participants) will be presented by treatment group and/or overall as appropriate, and listed by participant.

9.2 Protocol Deviations

Participant data will be examined for evidence of protocol deviations. All protocol deviations will be categorized and listed by participant.

9.3 Demographic and Baseline Characteristics

All demographic and baseline characteristics (including weight, height, and body mass index [BMI]) will be summarized overall, and they will be listed by participant.

Descriptive statistics (mean, standard deviation [SD], minimum [min], median, and maximum [max]) will be calculated for continuous variables, using the last results obtained prior to first study drug administration. Frequency counts and percentages will be tabulated for categorical variables.

9.4 Medical History

Medical history will be presented by participant in a data listing. The Medical Dictionary for Regulatory Activities (MedDRA) Version 25.0 will be used to classify all medical history findings by system organ class (SOC) and preferred term (PT).

9.5 Prior and Concomitant Medications

Prior medications are medications started before and ongoing at the time of ICF, or started at the time of ICF and in either case stopped prior to first study drug administration. Concomitant medications are medications started before and ongoing at the time of study drug administration, or started after first study drug administration. Both prior and concomitant medications will be listed by participant. The World Health Organization Drug Dictionary (WHO DD) Version B3, Mar 2022 will be used to define the anatomical therapeutic chemical (ATC) classification code (2nd level), and preferred name for each prior and concomitant medication. When 2nd level classification code is not available, 1st level classification will be used instead.

This document is confidential.

10 SAFETY ANALYSIS

Safety and tolerability analysis will be performed for all participants in the safety population. No inferential statistical analysis of safety data is planned.

Safety and tolerability to treatments will be evaluated through the assessment of adverse events (AEs), vital signs, 12-lead electrocardiograms (ECGs), and clinical laboratory parameters. Safety and tolerability data will be reported using descriptive statistics (mean, median, SD, Min, Max, and sample size).

10.1 Physical Examination Findings

Participants will undergo a complete physical examination at screening, and a brief physical examination on Day -1 of each period and at study exit. Individual results will be presented in a data listing.

Any abnormal findings judged to be clinically significant will be documented as medical history or as an AE, depending upon time of observation, as appropriate. Any physical examination findings documented as AEs will be included in AE summaries.

10.2 Adverse Events

AEs, which are collected from the time of enrollment, will be coded using the latest version of MedDRA (Version 25.0).

All AE summaries will be restricted to treatment-emergent adverse events (TEAEs) only. TEAEs will be defined as AEs that occur on or after the date and time of first study drug administration. Any AE that first occurs prior to first study drug administration but worsens in severity after the first study drug administration will also be considered a TEAE. Non-TEAEs are those that occur prior to the first administration of the study medication and resolved prior to dosing or that first occur prior to the first study drug administration, but do not worsen in severity after dosing. TEAEs will be attributed to the most recent study drug taken. A TEAE with a start date and time during the washout period (ending at the time of next study drug administration) will be attributed to the study drug taken during the previous treatment period (unless there was worsening following the next drug administration).

TEAEs will be summarized by treatment for the safety population. The number and percentage of participants experiencing TEAEs and the number of TEAEs will be tabulated. Participants who experience the same AE (in terms of MedDRA PT) more than once will only be counted once for that event, however, the total number of events will also be counted per category. This also applies to sub-categories and SOCs displayed in the summaries.

In each table, TEAEs will be sorted by SOC and PT in descending order of overall frequency. The following summaries will be presented:

- Overall summary of TEAEs

This document is confidential.

- TEAEs by SOC and PT
- TEAEs by SOC, PT, and maximum severity
- TEAEs by SOC, PT, and maximum relationship to study drug
- Serious TEAEs by SOC and PT

All AEs will be presented in data listings. This will include a separate listing of TEAEs, Non-TEAEs and serious AEs. AEs leading to discontinuation will also be listed separately.

10.3 Laboratory Parameters

Clinical laboratory tests, including biochemistry, hematology, and urinalysis will be performed at screening and at Day -1 of each period, and at study exit.

Biochemistry will include albumin, alkaline phosphatase (ALP), alanine transaminase (ALT), aspartate aminotransferase (AST), calcium, chloride, creatinine, creatine phosphokinase (CPK), estimated glomerular filtration rate (eGFR), calculated using the Modification of Diet in Renal Disease (MDRD) equation, gamma-glutamyl transferase (GGT), glucose, phosphorus, potassium, sodium, total, direct and indirect bilirubin, total protein, and urea (BUN). Considering that indirect bilirubin is calculated from total and direct bilirubin values, indirect bilirubin result would not be available in case of direct bilirubin below the limit of quantification. Hematology will include: haptoglobin, hematocrit, hemoglobin, platelet count, red blood cell (RBC) count, reticulocyte, and white blood cell (WBC) count and differential (basophils, eosinophils, lymphocytes, monocytes, neutrophils). Haptoglobin and reticulocyte count will be performed only in case of decrease in hemoglobin levels below the lower limit of normal (LLN) on Day -1 of each period and at study exit. Urinalysis will include bilirubin, blood (occult), color and appearance, glucose, ketones, leukocyte esterase, nitrite, pH, protein, specific gravity, urobilinogen, and microscopic examination (in the event of abnormal findings).

Coagulation tests (activated partial thromboplastin time [aPTT], international normalized ratio [INR] and prothrombin time [PT]) will be performed only in case of abnormal LFTs (i.e., ALP, AST, or ALT is >3 x upper limit of normal [ULN]) on Day -1 of each period and at study exit. The results will be listed if applicable.

Other laboratory assessments include serology tests, drug, cotinine, and alcohol screens, COVID-19 tests, and hormone screens (for female participants). Serology tests and follicle-stimulating hormone (FSH) levels will be measured at screening only. Drug, cotinine, and alcohol screens will be performed at screening and at Day -1 of each period. A COVID-19 test will be performed on Day -1 of each period. Pregnancy tests will be administered to females of childbearing potential at screening, Day -1 of each period, and at study exit. Results of urine drug screens, serology tests, pregnancy tests, alcohol breath tests, and urine cotinine tests will be listed.

Individual clinical laboratory results, change from baseline and reference ranges will be presented in data listings. Baseline will be defined as the last results (scheduled or unscheduled)

This document is confidential.

obtained prior to the first drug administration. Abnormal results will be flagged, as appropriate, in these listings. Clinically significant laboratory abnormalities will be identified as Grade 3 to 4 laboratory test results graded according to numeric laboratory test criteria in the latest version of Common Technical Criteria for Adverse Events (CTCAE), if available, otherwise, according to the latest version of Division of Acquired Immunodeficiency Syndrome (DAIDS) Table for Grading the Severity of Adult and Pediatric Adverse Events.

Additionally, a listing presenting abnormal LFTs (values greater than 3 times the upper limit of the normal [ULN] range for ALT, ALP or AST and values greater than 2 times ULN for total bilirubin) will be provided. An evaluation of drug-induced serious hepatotoxicity (eDISH) will be provided graphically. For this eDISH plot, the data will consist of the maximum values of ALT and total bilirubin that are observed at any time during or after dosing with zavegeptan.

